7.3 Definition of Analysis Populations

All-randomized (Intention To Treat-ITT) population

This population includes all randomized participants regardless of the actual treatment received. This population will be used for the primary analysis of the primary safety and efficacy endpoints.

Per protocol population

This population excludes participants who have not started the assigned therapy by the time of the 1 month telephone interview. For time-to-event analyses, participants who stop taking the assigned treatment will be censored after permanently stopping the assigned treatment.

7.4 Interim Analyses and Stopping Rules

There will be no formal interim analyses for the primary efficacy or safety endpoints for futility. The Data and Safety Monitoring Board (DSMB) will meet regularly to review patient safety and overall study conduct. The independent DSMB will review the summaries of patient safety and self-reported adherence at regular intervals.

Pooled event rates for the primary safety and primary efficacy and per-protocol anticoagulant adherence will be reviewed by the Steering Committee after 500, 1000, and 1500 participants have completed the 12-month telephone contact. The overall sample size will be assessed based on a comparison of the observed rates with the rates used for the sample size estimates.

7.5 Data Analyses

Baseline characteristics will be presented using mean (standard deviation) and median (25th, 75th percentiles) for continuous variables and as frequencies (percentages) for categorical variables. No formal comparisons will be computed for baseline variables.

The primary analyses for safety primary endpoint will be based on an un-stratified Cox model adjusting for the two treatment indicators and three stratification indicators. The ascertainment time will be based on the time of the first event or censoring time. Stratification will be based on the anticoagulant used during the screening period. The all-randomized (ITT) analysis dataset will be used for the primary analyses. The treatment effect for each DOAC compared to warfarin will be computed using the estimated hazard ratio and associated 95% confidence intervals. Secondary analyses will be based on a Kaplan-Meier estimates on the all-randomized (ITT) and per-protocol populations.

For the efficacy primary endpoint, the primary analysis will be based on a Kaplan-Meier analysis using the all-randomized (ITT) analysis dataset. The 12-month event rates differences between the DOACs versus warfarin will be based on the difference in the Kaplan-Meier estimates and the one-sided upper 95% confidence interval will be based on a bootstrap estimator. Secondary analyses of the recurrent VTE endpoint will be based on the Cox regression model. Exploratory analyses will directly compare the two DOACs for both safety and efficacy endpoints. Additionally, an exploratory analysis will pool the two DOAC arms and compare those estimates with the warfarin treatment group.

For secondary endpoints, the estimated differences between the DOACs and warfarin treated groups will be based on linear models, logistic regression, and Cox models depending on the endpoint. Efforts will be made to limit the amount of missing data for the key endpoints and adherence measures. When necessary, multiple imputation will be used to account for missing covariate information.

The SAP will contain details on sensitivity analysis that will be done to support the previously described analyses. There are two particular issues that might create biased estimates – missing data and lack of adherence to the assigned treatment. For the missing data problem, we will impute data with higher, same, and lower event rates for the DOAC arms to estimate the impact of missingness on the study results. In addition to the analyses with the all randomized dataset, we will conduct analyses with the per-protocol dataset to determine the impact of participants not taking the assigned study drug. For the per-protocol analyses there is no guarantee that the comparisons are valid based on randomization. To account for this potential bias, inverse probability weighted (IPW) estimators will be used to re-weight the per-protocol population. The IPW weights will be obtained using logistic regression models predicting adherence at 1 month. The SAP will also address analysis of the Patient Reported Outcomes tools, the ACTS and the EQ-5D-5L.

The study investigators have identified several pre-specified subgroups of interest. Those subgroups include: initial anticoagulant, race, sex, renal impairment, obesity, and antiplatelet use (Buckner 2012; Liao 2014; White 2009). Given the expected low number of events for both primary endpoints, the subgroups will need to be interpreted

cautiously. For each subgroup we will compute an interaction p-value and then estimate hazard ratios for each subgroup.

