7. STATISTICAL CONSIDERATIONS

7.1 General Design Issues

COVET is a 3-arm prospective, multi-center, open-label, active comparator, randomized study designed to compare the efficacy and safety of apixaban and rivaroxaban compared with standard warfarin therapy. All potential study endpoints will be reviewed by a central adjudication committee that is blinded to treatment assignment. For participants who withdraw consent for follow-up, all data obtained prior to the time of formal withdrawal will be used in data analyses. The duration of follow up from randomization is expected to be twelve months, and all participants will be expected to remain in study until the 12-month follow-up telephone call regardless of whether they are taking their assigned study medication. Reporting of this prospective, randomized, open-label, blinded endpoint design will follow the CONSORT recommendations (Hansson 1992; Paggio 2012).

The primary efficacy endpoint is rate of recurrent VTEs and the primary safety endpoint is clinically relevant bleeding. Secondary endpoints include components of the primary endpoints, all-cause mortality, and other events of interest. The primary efficacy and safety endpoints will be confirmed by a CEC. Participants will be randomized in a 1:1:1 ratio to warfarin, apixaban, or rivaroxaban. Randomization will be stratified by the anticoagulant used during the screening period. For purposes of randomization, the screening anticoagulants will be classified as either warfarin, apixaban, rivaroxaban, or other. The relative open inclusion criteria, limited exclusions, and simple follow-up structure of COVET are an attempt to be pragmatic (Thorpe 2009).

SAS software version 9.4 or higher will be used for all statistical analyses. P-values less than 0.05 will be considered statistically significant unless otherwise specified. Complete details of all planned analyses will be contained in a separate Statistical Analysis Plan (SAP). The SAP will include the planned tables, listings, and figures. In particular, special attention will be given the participants who do not have complete data.

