7.2 Sample Size Justification

The planning and sample size calculations for the COVET study were designed to compare warfarin vs. apixaban and warfarin vs. rivaroxaban. A direct exploratory and descriptive comparison of the two DOACs will be conducted but the study was not powered to detect statistically significant differences between those treatment groups.

For the primary safety endpoint, there will be two comparisons, apixaban versus warfarin and rivaroxaban versus warfarin, each of which will be tested at the two-sided 0.05 level of significance to detect a 50% reduction (HR=0.50) in clinically relevant bleeding compared to warfarin. For the primary efficacy endpoint, there will be two comparisons, apixaban versus warfarin and rivaroxaban versus warfarin to determine if the DOACs are non-inferior to warfarin in the prevention of recurrent venous thromboembolism. The non-inferiority assessments will be based on comparing the one-sided 95% upper confidence interval with a 2% absolute risk increase for recurrent VTE.

The type I error rates for the non-inferiority and superiority analyses have been set at 0.05 one-sided and 0.05 two-sided, respectively. These are considered standard values for two

arm studies. We have elected to not alter them for this three-arm design because the clinical questions of interest are the two comparisons of the DOACs versus warfarin.

For the primary efficacy analysis, using an outcome of recurrent VTE, we expect 12-month rate of 0.87% for the warfarin arm compared with 1.5% for the DOACs (Einstein Investigators 2010; Agnelli 2013). Sample sizes of 950 per arm are sufficient to provide 80% power to have the upper 95% one-sided confidence interval less than 2%. The proposed sample size of 1000 participants per arm allows for 5% missing data due to loss-to-follow-up, deaths not related to VTE, and lack of starting the assigned study drug. These calculations were obtained using a simulation method with nQuery Advisor 7.0 software.

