9.1 General Analysis Conventions

9.1.1 Statistical significance

Statistical comparisons will be performed using two-sided significance tests. The level of significance for all secondary efficacy and safety analyses will be set at an alpha level of 0.05.

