9.3 Analysis of Time to “Response” Data

9.3.1 Primary and Secondary Endpoint Analysis

The primary analyses for safety primary endpoint will be based on a stratified Cox model. The ascertainment time will be based on the time of the first event or censoring time. Stratification will be based on the anticoagulant used during the screening period. The all-randomized analysis dataset will be used for the primary analyses. The treatment effect for each DOAC compared to warfarin will be computed using the estimated hazard ratio and

associated 95% confidence intervals. Secondary analyses will be based on a Kaplan-Meier estimates on the all-randomized and per-protocol populations.

For the efficacy primary endpoint, the primary analysis will be based on a Kaplan-Meier analysis using the all-randomized analysis dataset. The 12-month event rates differences between the DOACs versus warfarin will be based on the difference in the Kaplan-Meier estimates and the one-sided upper 95% confidence interval will be based on a bootstrap estimator. Secondary analyses of the recurrent VTE endpoint will be based on the Cox regression model. Exploratory analyses will directly compare the two DOACs for both safety and efficacy endpoints. Additionally, an exploratory analysis will pool the two DOAC arms and compare those estimates with the warfarin treatment group.

For secondary endpoints, the estimated differences between the DOACs and warfarin treated groups will be based on linear models, logistic regression, and Cox models depending on the endpoint. Efforts will be made to limit the amount of missing data for the key endpoints and adherence measures. When necessary, multiple imputation will be used to account for missing covariate information.

References

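### Does leaving the bootstrap type unnamed put the non-inferiority verdict at risk?

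*Protocol*

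**What the plan says.** Protocol 7.2 sets the level: "The type I error rates for the non-inferiority and superiority analyses have been set at 0.05 one-sided and 0.05 two-sided, respectively". It describes the decision as "comparing the one-sided 95% upper confidence interval with a 2% absolute risk increase for recurrent VTE", and its power statement requires the upper limit to be less than 2%. On the planning rates, "we expect 12-month rate of 0.87% for the warfarin arm compared with 1.5% for the DOACs", with 950 evaluable per arm (1000 randomised, 5% missing) and 80% power. On how that power was found it says only "These calculations were obtained using a simulation method with nQuery Advisor 7.0 software", so the interval behind the simulation is not named.

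Protocol 7.5 names the all-randomised population and the Kaplan-Meier difference at 12 months, and says that "the one-sided upper 95% confidence interval will be based on a bootstrap estimator". Protocol 7.1 defers full analysis details to the SAP. SAP 9.3.1 again has the "difference in the Kaplan-Meier estimates and the one-sided upper 95% confidence interval will be based on a bootstrap estimator" and adds nothing on type, resampling scheme, number of resamples or seed. SAP 9.1.1 states that "Statistical comparisons will be performed using two-sided significance tests", while SAP section 7 repeats the one-sided 0.05 level for non-inferiority.

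**The concern.** The bootstrap is a family of methods. Percentile, basic, BCa, studentized and normal-type limits (bootstrap standard error with a normal quantile) agree in large samples but can differ when events are few. Here the expected counts are 950 × 0.0087 = 8.3 on warfarin and 950 × 0.015 = 14.3 on a DOAC.

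If the types differ, two things follow. The realised false non-inferiority rate depends on a choice that the plan does not record. In an open-label trial, a choice made late could also settle a borderline verdict, and there are two such verdicts. The SAP was the place promised for this detail and does not give it.

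**Working it through.** **Inputs.** Warfarin 0.87%, DOAC 1.5%, margin 2 points, one-sided 0.05, 950 per arm, 80% power (Protocol 7.2). Drug-specific rates of 1.3% for rivaroxaban and 1.7% for apixaban 2.5 mg (Protocol 1.3, Table 1). Assumed: a DOAC rate of 2.0% as an extra scenario, and 5% uniform loss in the simulations.

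**Step 1: the plan's own figure.** The unpooled Wald formula gives

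- variance sum = 0.0087 × 0.9913 + 0.015 × 0.985 = 0.02340
- SE = √(0.02340 / 950) = 0.00496
- power = Φ((0.02 − 0.0063) / 0.00496 − 1.645) = Φ(1.116) = 86.8%

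This is above the stated 80%. Exact power by enumeration is 81.4% for the Farrington-Manning score limit, 81.5% for Newcombe and 81.1% for Wald with continuity correction. So the stated 80% reproduces at one-sided 0.05 with ordinary interval methods.

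**Step 2: exact comparison of bootstrap types.** With complete follow-up the Kaplan-Meier estimate is the simple proportion. For observed counts (x_w, x_d), patients resampled within arm give binomial counts with n = 950 and the observed proportions, so the bootstrap distribution of the difference D* is exact. With d the observed difference, the upper limits are

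- percentile: 95th percentile of D*
- basic: 2d − 5th percentile of D*
- normal-type: d + 1.645 × bootstrap SE
- BCa: percentile of D* at level Φ(z0 + (z0 + 1.645) / (1 − a(z0 + 1.645))), where z0 is the bias correction and a the acceleration
- studentized: from the bootstrap t distribution

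The chance of declaring non-inferiority is the sum of Pr(x_w) × Pr(x_d) over all pairs whose limit is below 0.02.

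| Type | Power (0.87% v 1.5%) | False non-inferiority (0.87% v 2.87%) |
|---|---|---|
| BCa, ties split | 81.4% | 4.6% |
| Percentile | 82.9% | 5.1% |
| Studentized | 83.6% | 5.3% |
| Basic | 83.7% | 5.1% |
| Normal-type | 85.8% | 6.1% |
| BCa, strict tie rule | 85.7% | 6.5% |

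The two BCa rows differ only in whether resamples equal to the estimate count half or not at all in z0.

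**Step 3: how often the verdict changes.** Any disagreement among percentile, basic, normal-type and BCa (ties split), warfarin 0.87%:

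| True DOAC rate | Disagreement |
|---|---|
| 0.87% | 0.2% |
| 1.3% | 2.5% |
| 1.5% | 4.4% |
| 1.7% | 5.9% |
| 2.0% (assumed) | 6.3% |
| 2.87% (margin) | 1.5% |

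The peak is about 6.4%, near 1.85%. At the planning rates the pairwise figures are percentile v basic 0.8%, percentile v BCa 1.5%, percentile v normal-type 2.9% and normal-type v BCa 4.4%.

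**Step 4: a bound on late choice.** At the margin, 6.14% − 4.61% = 1.53%, which equals the disagreement rate. The four verdicts are therefore nested there. Always picking the most favourable of the four gives 6.1%, about 1.1 points above nominal.

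**Step 5: sensitivity.** With other assumed warfarin rates (950 per arm, complete follow-up), error is 4.6–6.6% at 0.5% and 4.7–5.6% at 1.5%. Three Kaplan-Meier simulations with 1000 per arm and 5% uniform loss gave 4.9–5.9%, 5.6–6.6% and 5.7–6.8% (Monte Carlo SE about 0.3 points each). They do not fully agree, and the loss pattern is assumed in all three. In the second, disagreement at the margin was 1.35% and the lowest error 5.62%, so the most favourable choice gives at most 5.62% + 1.35% = 7.0%. Simulated power at the planning rates was 83.7–86.9%.

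**The case for a change.** The best case for acting is that the gap is undisputed, both primary efficacy verdicts depend on it, and a few sentences would close it. At the apixaban rate in the Protocol's own Table 1, 5.9% of comparisons would turn on the type. Stating the type in advance removes any question about when it was chosen.

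Much of that stands as good practice. Three parts do not carry the weight put on them.

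- **The disagreement rate depends on the scenario.** It ranges from 0.2% to about 6.4%, and it is only 1.5% at the margin, where the error rate is measured. Most of it is one pair, normal-type against BCa.
- **BCa is not a clear remedy.** Its error moves from 4.6% to 6.5% with the tie rule alone, and two of the three simulations with loss put it at 5.6–5.7%. Naming BCa without a tie rule would leave similar freedom. An illustration with 8 v 18 events (percentile limit 18/950 = 1.89%, BCa 19/950 = 2.00%) works only because 0.02 × 950 is exactly 19 events; under the strict tie rule BCa also gives 1.89%.
- **The related requests add little.** Protocol 7.2 already asks for a limit below 2%. SAP section 7 already sets the one-sided level, so the general sentence in SAP 9.1.1 misleads no one about this test. An additional two-sided interval is a reporting preference.

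**Conclusion.** The concern is accurate about the text but does not call for a change. The plan fixes what determines the result: population, estimand, time point, margin, one-sided level and use of a bootstrap limit. What is missing is an implementation detail that a trial statistician settles in the programming specification, with patients resampled within arm as the natural scheme.

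With 950 per arm, complete follow-up and 0.87% on warfarin, the common types have an error of 4.6–6.1% (6.5% for BCa with the strict tie rule), and all exceed the stated 80% power. Under an assumed 5% uniform loss, error is about 5–7%, with some unexplained variation between simulations. The residual risk is a borderline result: about 4.4% of comparisons at the planning rates, and at worst roughly 1 to 2 points of extra error if the most favourable of the four types were picked late. That is a tidiness point. No alternative was shown to perform better than an ordinary reading of what is written.

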8. FOLLOW-UP DATA COLLECTION AND CLINICAL EVENT CLASSIFICATION

Participants will be provided with instructions to maintain a diary during the course of the study to facilitate reporting of events at the time of the follow-up calls. For participants in the US, the DCRI Call Center will attempt phone calls at 1 month, 6 months and 12 months following randomization. For participants enrolled at Canadian sites, the enrolling site will contact the participant at the same time intervals. Information collected during these phone calls will be documented in the eCRF. If a participant reports that they are experiencing an event during a scheduled call, the Call Center agent will advise the participant to contact their health care provider or call 911 if it is an emergency. The event details would be captured at the next scheduled call. Medical records associated with all potential outcome events will be requested/obtained and sent to the blinded CEC for review.

COVET is comparing treatment strategies that are already in standard clinical use, and it is not anticipated that outcomes beyond those that can be seen in any patient taking anticoagulant therapy will be encountered. For each outcome event, supporting documentation to include all radiographic imaging data, relevant laboratory data, and treatment records will be collected by the centralized call center for review and validation. All outcomes will be independently adjudicated by physician reviewers with expertise in thrombosis who will be blinded to the specific treatment arm to which the patient had been randomized. Outcome classification will follow an established protocol similar to prior studies conducted through the DCRI. Details of the clinical event adjudication process will be included in the CEC Charter.

9. DATA MANAGEMENT AND QUALITY ASSURANCE

9.1 Data Management

All required data for this study will be entered into the electronic case report form (eCRF). This study will use Web-based e-CRFs developed through a validated, electronic reporting-electronic-signatures-compliant platform (21 Code of Federal Regulations Part 11). For security reasons, and in compliance with regulatory guidelines, it is imperative that only the persons who own the user IDs and passwords access the system using their own unique access codes. Access codes are nontransferable. Site personnel who have not undergone training may not use the system and will not be issued user ID and password until appropriate training is completed.

At the conclusion of the study, each enrolling site will be provided with a compact disc containing PDF files of both the individual patient's data and the audit trail (changes made to the database). This will be maintained at the site according to the requirements for records retention.

Computerized data will be accessible only by password, and a centralized monitoring system will record and report all access to data. The DCRI computer network is protected by a firewall. To ensure participant anonymity, eCRFs will be identified by study number only. No participant identifiers will be used in the presentation of data. Except when required by law, participants will not be identified by name, personal identification number (e.g. social security number, social insurance number), address, telephone number, or any other direct personal identifier in study records. This information will be retained by each individual center and will not be disclosed to the DCRI except as needed for centralized follow-up of the participants. Participants will be informed that their records may be reviewed in order to meet federal, state or regional/local regulations. Reviewers may include the study monitors, IRBs or Ethics Committees, and other government regulators as dictated by local law, or their delegates.

Records of patients, source documents, monitoring visit logs, eCRFs, inventory of study product, regulatory documents, and other sponsor correspondence pertaining to the study must be kept in the appropriate study files at the site. Source documents include all recordings and observations or notations of clinical activities and all reports and records necessary for the evaluation and reconstruction of the clinical study. These records will be retained in a secure file for the period required by the institution or site policy. Prior to transfer or destruction of these records, the DCC must be notified in writing and be given the opportunity to further store such records.

9.2 Quality Assurance

Steps to be taken to ensure the accuracy and reliability of data include:

- the selection of qualified investigators and appropriate study centers
- review of protocol procedures with the investigator and associated personnel before the study
- periodic monitoring visits to clinical sites

- electronic CRF completion guidelines will be provided and reviewed with study personnel before the start of the study.
- The DCRI clinical research associate will review eCRFs for accuracy and completeness during site monitoring; any discrepancies will be resolved with the investigator or designee, as appropriate.

At regular intervals, all data will be transferred from the study database to SAS for statistical summarization, data description, and data analysis. Further cross-checking of the data will be performed in SAS, and discrepant observations flagged and appropriately resolved through a data query system.

